#### **9.7.1.3.2. Medical and Surgical History**

Medical and surgical history will be coded using the Medical Dictionary for Regulatory Activities (MedDRA, Mozzicato, 2009). The frequency and percentage of subjects with any medical and/or surgical history was summarized by treatment group using the FAS. System organ class (SOC) will be sorted alphabetically and preferred term (PT) within each SOC will be sorted by overall descending order of frequency according to the following rules in order:

1. Descending frequency within High Dose;
2. Descending frequency within Low Dose;
3. Descending frequency within Vehicle;
4. PT in alphabetical order.

The medical and surgical history will include both the ocular and the general (non-ocular) history. Ocular medical history, ocular surgical history, general (non-ocular) medical history and general (non-ocular) surgical history will be summarized separately. Ocular and non-ocular medical and surgical histories are identified according to which CRF the event is recorded. Ocular medical history will be summarized separately for study eye and non-study eye

#### **9.7.1.3.3. Prior and Concomitant Medications**

Prior and concomitant medications will be coded using the World Health Organization Drug Dictionary (B3 WHO Drug Global, Lagerlund et al., 2020) for anatomical therapeutic chemical classification (ATC) and preferred drug name.

The frequency and percentage of subjects with coded medications will be summarized by treatment group using the Safety Analysis Set. A subject who used multiple medications was counted only once for each ATC and preferred drug name. Therapeutic Subgroup is sorted alphabetically, and preferred term is sorted by descending frequency overall within each Level 3 term according to:

1. Descending frequency within High Dose;

---

2. Descending frequency within Low Dose;
3. Descending frequency within Vehicle;
4. PT in alphabetical order.

Prior and concomitant medications will be summarized separately. Ocular medications are defined as those medications for which an eye has been specified (OD, OS, or OU). Ocular and non-ocular medications will be summarized separately. Ocular medications will be summarized separately for study eye and non-study eye.

Prior medications are defined as any medications that started and stopped prior to the date of cataract surgery. Concomitant medications are defined as any medications that are ongoing or start after the start of cataract surgery, including medications provided at Visit 2 (Day of Surgery) as part of the cataract surgery, through the end of study/exit from study visit. Medications taken after Visit 7 or withdrawal from the study are not considered concomitant.

#### **9.7.1.4. Analysis of Study Medication Compliance and Exposure**

Treatment adherence and exposure will be assessed by the data from the Study Drug Administration and Treatment Adherence eCRFs and will be summarized by treatment group using the Safety Analysis Set.

Treatment adherence was assessed by 5 questions: Did subject return IP at this visit, and if so, how many used vitals and how many un-used vials, did subject miss any doses since the last visit, and if so, how many doses missed. Descriptive statistics will be presented for these measures by visit by treatment group.

Duration of exposure of double-masked study drug will be calculated as the total number of days from the first double-masked dose date to the last double-masked dose date plus 1 (one) regardless of temporary dose interruptions.

#### **9.7.1.5. Analysis of Efficacy**

Summary descriptive statistics will be presented for all study visits at which efficacy data are collected. Efficacy analyses will be presented by the study eye.

For subjects who discontinue treatment prior to the Visit 7, the data collected on the Early Termination eCRFs will not be summarized unless the termination within the visit windows of a particular visit.

All longitudinal models will be fit using the MIXED procedure in SAS. Categorical analyses will be conducted using the FREQ procedure.

Secondary and exploratory endpoints will be analyzed in a similar manner to the primary endpoint regardless of the significance of the primary endpoint analysis. All efficacy analyses will be conducted using the FAS and PP Analysis Sets.

### 9.7.1.5.1. Primary Efficacy Analysis

Primary Estimand: The primary estimand is treatment difference between VVN461 (1.0% or 0.5%) and the Vehicle in the proportion of subjects with ACC Grade 0 at Visit 6 (Day 14) in the study eye using the FAS.

Target Population: Subjects undergoing routine cataract surgery who meet the study entry criteria.

Endpoint: Proportion of subjects with ACC Grade 0 in the study eye at Visit 6 (Day 14).

Treatment Condition: Treatment condition is based on randomized treatment.

Population-Level Summary: The difference in proportions in subjects with ACC Grade 0 in the study eye at Visit 6 (Day 14) and the corresponding p-value.

#### Intercurrent Events and Strategies to Address Intercurrent Events

- Discontinuation of study therapy with continued participation in the study without receipt of rescue therapy
  - Treatment Policy Approach – no imputation; use observed data
- Receipt of rescue therapy (topical corticosteroid) in the study eye
  - Composite Approach – subjects who receive rescue therapy ~~at or~~ before the assessment visit will be assumed to have failed the primary endpoint
- Missing data due to discontinuation due to Lack of Efficacy or Adverse Event
  - Composite Approach – subjects who discontinue due to Lack of Efficacy or Adverse Event before the assessment visit will be assumed to have failed the primary endpoint
- Missing data with or without withdrawal, regardless of reason
  - Hypothetical Approach – no imputation; analysis will be based on subjects who have an evaluable anterior chamber in the study eye at Visit 6 (Day 14)

Pearson's chi-square will be used to test the primary endpoint between the 2 different doses of VVN461 vs the Vehicle. Analyses will be also performed on observed data without failure criteria for rescue. These analyses will also be performed on the PP Analysis Set.

A sensitivity analysis with control-based multiple imputation method will be carried out in the following three steps:

- 1) Imputation: Missing binary data will be filled in 25 different times to generate 25 imputed datasets. The following code will be used to impute the 25 datasets with data of subjects prior to rescue medications.

[figure not shown]
The control is where treatment = 3. This imputes data for all arms according to the control treatment.

- 2) Analysis: Each of the 25 imputed datasets will be analyzed at Visit 6 using PROC FREQ where the proportions of responders in each treatment arm will be calculated:

[figure not shown]

- 3) Pooling: The results from the 25 imputed datasets will be combined for estimation using PROC MIANALYZE.

Results will include treatment arm proportions:

As well the difference between proportions:

The sensitivity analyses will only be performed on the primary endpoint at Visit 6. All analyses will each be performed with the FAS and Per Protocol Analysis Sets.

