#### **9.5.1.2.3. Prior and Concomitant Medications**

All medications that the subject has taken within 30 days before Visit 1 (Screening) and through Visit 7 (Day 21; End of Study) or exit from the study will be recorded in the eCRF and the subject's source documents. Subjects will be asked for details about any changes in documented medications at all visits. The generic name of the drug, dose, route of administration, duration of treatment (including start and stop dates), frequency, indication, and whether or not the medication was taken due to an AE or as rescue will be recorded for each medication. Prior and concomitant medications will be coded using the World Health Organization Drug Dictionary (WHODrug). Restricted and prohibited prior and concomitant therapy are outlined in the protocol.

Subjects are eligible to be rescued at any time at the Investigator's discretion and placed on appropriate treatment or therapy. Although the use of rescue medication is allowable at any time, advance consultation with the Medical Monitor is preferred, if possible. If a delay in rescue would place the subject at unnecessary risk, the Investigator should proceed with rescue immediately.

The date of rescue medication administration, as well as the name of the rescue medication and dosage regimen, must be recorded as concomitant medications in the eCRF, with a note indicating that the medication was used for rescue. Subjects who require rescue will be counted as treatment failures and undergo follow-up safety assessments and procedures. Every attempt should be made to have subjects continue in the study for safety evaluations, even if subjects discontinue IP. The need for rescue medication itself will not be considered an AE.

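### Could the SAP's control-based multiple imputation turn rescued subjects into responders?

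*SAP*

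**What the plan says.** SAP 9.7.1.5.1 tests the primary endpoint with Pearson's chi-square on the FAS. Subjects who receive rescue therapy before the assessment visit are treated as failures. A second composite rule, headed "Missing data due to discontinuation due to Lack of Efficacy or Adverse Event", reads: "subjects who discontinue due to Lack of Efficacy or Adverse Event before the assessment visit will be assumed to have failed the primary endpoint". Other missing Visit 6 values are not imputed.

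The section then adds analyses around the primary one. The first is announced as "Analyses will be also performed on observed data without failure criteria for rescue". The second is the control-based multiple imputation, whose first step says: "Missing binary data will be filled in 25 different times to generate 25 imputed datasets". The next sentence is "The following code will be used to impute the 25 datasets with data of subjects prior to rescue medications", followed by a code listing that appears in the text copy only as an image placeholder. After it comes the donor rule: "This imputes data for all arms according to the control treatment". The imputed datasets are analysed at Visit 6 and pooled.

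Two other places matter. SAP 9.5.1.2.3 says, as protocol 5.5.2 does: "Subjects who require rescue will be counted as treatment failures". Protocol 9.4.2 says that efficacy analyses use only data from before the first rescue and that later data are blanked.

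**The concern.** Two readings of the imputation step are possible.

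- **Failures first.** Rescued subjects and those who stop for lack of efficacy or an adverse event are coded as non-responders. Only Visit 6 values missing for other reasons are imputed from Vehicle.
- **Rescue imputed.** Post-rescue values are blank, count as missing, and are drawn from Vehicle. A rescued subject can then be a responder in some of the 25 datasets.

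The second reading has some textual support. The imputation sentence refers to data before rescue, protocol 9.4.2 blanks data after rescue, and SAP 9.7.1.5.3 uses similar wording for the repeated-measures models, where post-rescue records are left out.

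Under that reading the analysis would estimate what happens if nobody were rescued, whereas the primary analysis counts rescue as failure. A gap between the two results would mix the effect of drop-out with the re-scoring of rescued subjects. This imputation is also the only listed analysis that varies the handling of the remaining missing values while it could keep the failure rules, so a blurred result would weaken the one direct check on drop-out.

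**Working it through.** **1. The plan's own figures.** SAP 9.7.2 gives 30 per arm, 30% against 65%, two-sided 0.05 and Pearson chi-square, with 80% power. The normal approximation gives 79.0% and exact enumeration of the uncorrected test gives 79.8%. With 10% drop-out, 30/0.9 = 33.3, so 34 per arm and 102 in total. Both figures reproduce.

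**2. The text, side by side.**

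| Place | What it implies for a rescued subject |
|---|---|
| SAP 9.7.1.5.1, composite rule | Has an assigned failure |
| SAP 9.5.1.2.3 and protocol 5.5.2 | Counted as a treatment failure |
| SAP 9.7.1.5.1, extra observed-data analysis | The rescue rule is dropped, and the SAP says so |
| SAP 9.7.1.5.1, imputation step 1 | Fills missing binary values, using data before rescue |
| Protocol 9.4.2 | Later data are blanked |
| SAP 9.7.1.5 | Repeats the protocol's opening on descriptive summaries but not the blanking sentence |
| SAP 9.7.1.5.3 | Concerns graded outcomes, which have no failure value |

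A subject with an assigned failure has a binary value, so nothing is missing for the imputation to fill. The protocol's blanking sentence can stand beside the composite rule: the measured grade is blanked and the rule supplies the response status. If blanking also removed the response status, it would cancel the rescue rule in protocol 9.4.2.1, because missing values are left out of that analysis. The pre-rescue wording may simply describe which earlier-visit records feed the imputation model.

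**3. Size if the other reading were used.** From SAP 9.7.2: Vehicle 30%, active 65%, drop-out d = 0.10 (taken as unrelated to outcome). Assumed, because the documents do not give them: rescue rates rV (Vehicle) and rA (active), and k, the imputed success of rescued subjects relative to non-rescued Vehicle subjects. Non-rescued Vehicle success is q = 0.30/(1 − rV).

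Failures first: Vehicle 0.30; active 0.9 × 0.65 + 0.1 × 0.30 = 0.615; difference 0.315.

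Rescue imputed: each arm is (1 − d)p + (1 − d)·r·k·q + d·q, where p and r are that arm's response and rescue rates. The last term is the same in both arms, so the difference is (1 − d)[0.35 + (rA − rV)·k·q]. For 30%/10%, q = 0.30/0.70 = 0.4286. With k = 1 the difference is 0.9 × (0.35 − 0.2 × 0.4286) = 0.238.

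The last two columns come from 20,000 simulated trials per setting, with 34 per arm, 25 imputations, the Vehicle rate drawn from a Beta posterior, and pooling by Rubin's rules. They show how often the 95% interval excludes 0 in favour of VVN461. The failures-first figure is about 76%.

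| Rescue, Vehicle/active | Difference, k = 1 | Difference, k = 0.5 | Excludes 0, k = 1 | Excludes 0, k = 0.5 |
|---|---|---|---|---|
| 10%/5% | 30.0 | 30.8 | 69% | 72% |
| 20%/5% | 26.4 | 29.0 | 55% | 65% |
| 30%/10% | 23.8 | 27.6 | 42% | 58% |
| 40%/10% | 18.0 | 24.8 | 24% | 46% |
| 20%/20% | 31.5 | 31.5 | 72% | 73% |
| 5%/20% | 35.8 | 33.6 | 87% | 81% |

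At k = 0.25 the formula runs from 0.9 × (0.35 − 0.3 × 0.25 × 0.5) = 28.1 points (40%/10%) to 0.9 × (0.35 + 0.15 × 0.25 × 0.3158) = 32.6 points (5%/20%), close to 31.5.

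**4. The primary analysis.** On subjects with Visit 6 data, the primary test has an expected difference of 35 points and about 80% power in every row, because it never imputes.

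**The case for a change.** The protocol does not mention this imputation, so SAP 9.7.1.5.1 is its only description, and no readable sentence gives the order of the two steps. SAP 9.8.2, which lists departures from the protocol, names only pain-scale analyses. The protocol's blanking sentence has therefore not been formally withdrawn. Someone working from the text alone could follow it literally, and a choice between the readings after unmasking could be called data-driven. With much more rescue on Vehicle, the difference could fall from 31.5 to 18.0 points.

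What stands is that the prose is incomplete and that the readings can give different numbers. What does not stand is that the plan leaves the step undefined, because it refers to code for exactly this step. The largest shifts also need k = 1, where rescued subjects respond as often as Vehicle subjects who never needed rescue (50% in the 40%/10% case). An imputation model that uses poor pre-rescue grades would give a lower k. The SAP sets no success threshold for this analysis, so the interval percentages describe how it would look and decide nothing. For discontinuations due to lack of efficacy or an adverse event the case is weaker still. The failure rule is explicit, and the doubt rests on the heading and on silence.

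**Conclusion.** The concern does not call for a change. The missing detail belongs to the code, and the prose that can be read points to failures first on several counts, against one phrase in the SAP and a general protocol sentence that the SAP does not repeat. Confirming that failures are coded before imputation is part of ordinary program checking.

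If the other reading were used, the imputed difference would be 18.0 to 35.8 points instead of 31.5 over the assumed rescue rates. It would be lower when rescue is commoner on Vehicle, unchanged when the rates are equal, and higher when rescue is commoner on active. These figures rest on assumed rescue rates and an assumed k, and leave out discontinuations for lack of efficacy or an adverse event. Only the reading of robustness is exposed: the primary test, the hierarchy of the two dose comparisons and the sample size are unaffected.

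A separate point gives this one no weight. The composite rule ties rescue to topical corticosteroid, while SAP 9.5.1.2.3 and protocol 5.5.2 describe subjects "placed on appropriate treatment or therapy" at the investigator's discretion. Protocol 9.4.2.1 and the SAP synopsis also include rescue at the assessment visit itself, whereas SAP 9.7.1.5.1 strikes those words out. These passages must be reconciled with one another; no effect on a result has been shown.

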#### 9.7.1.5.2. Secondary Efficacy Analyses

The secondary efficacy endpoints include the following:

- Proportion of subjects with ACC Grade 0 in the study eye at Visit 5 (Day 7)
- Proportion of subjects with anterior chamber flare (ACF) Grade 0 in the study eye at Visit 6 (Day 14)
- Proportion of subjects with ACF Grade 0 in the study eye at Visit 5 (Day 7)
- Proportion of subjects requiring rescue medication before Visit 6 (Day 14)

### 9.7.1.5.3. Exploratory Efficacy Analysis

Exploratory endpoints will include the proportion of subjects with no postoperative ocular pain (NPRS = 0) in the study eye at Visit 5 (Day 7) and at Visit 6 (Day 14).

Observed mean NPRS prior to rescue mediation will also be analyzed at each given visit.

The following study eye endpoints will be analyzed at each visit using a mixed model repeated measures:

- 1) Mean CFB in ACC Grade
- 2) Mean CFB in ACF Grade
- 3) Mean NPRS

The model will include treatment, visit, and treatment by visit interaction as fixed effects and a covariate for baseline measurement (where appropriate) with a random effect for site. An unstructured covariance among repeated measurements will be assumed. If the model fails to converge using this covariance structure, spatial power or compound symmetry will be implemented in this order until convergence is reached. If convergence is not reached, values will be denoted as “--”. Only data from before the use of rescue medication will be included in these analyses.

run;

### 9.7.1.6. Analysis of Safety

Safety will be evaluated by AEs, changes from baseline in IOP measurements and Best Corrected Visual Acuity (BCVA), as well as, Slit Lamp Biomicroscopy and Dilated Ophthalmoscopy Exams.

The Safety Analysis Set will be used for all safety analyses. All data, including data after rescue therapy, will be summarized as observed and no data imputation will be performed. No statistical treatment group comparisons will be performed, unless otherwise specified. Analyses will be presented by study eye and non-study eye, if applicable.

For by visit summaries, data collected using Early Termination eCRFs will not be summarized unless the termination occurred within the visit windows of a particular visit.

All visits will be included in listings.

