7.1.9 Early Termination

In the event that a subject withdraws or is terminated from the study before the end of the study, every attempt will be made to ensure that the subject returns to the site as soon as possible and completes the Visit 7 (End of Study; Early Termination) assessments before being discharged from the study. Any unused IP should be collected during an early termination visit.

CONFIDENTIAL

8 Study Assessments

The Schedule of Procedures and Assessments ([Appendix 1](#): Schedule of Procedures and Assessment) provides a list of study assessments and evaluations to be performed and the timing of each.

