### Visit Windows

The nominal visits listed in the CRF will be used in the summaries. In general, unscheduled visits will not be summarized in tables unless otherwise noted.

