#### **9.7.1.6.4. Dilated Ophthalmoscopy (Fundus Exam)**

The frequency and percentage of subjects with observed values of each category as well as the categorical shift from baseline at each post-baseline visit will be tabulated at each scheduled visit for the study eye and non-study eye. The percentages are calculated based on the number of subjects at each visit in each treatment group based on non-missing observations of the Safety Analysis Set. The percentages for the shift will be calculated based on the number of subjects with both baseline and post-baseline values.

Descriptive summaries of the observed cup-to-disc ratio at each scheduled visit as well as the change from baseline at each post-baseline visit will be presented for both eyes.

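### Early-termination exams outside every visit window, and in general unscheduled exams, reach only the listings, so an early leaver's only post-dose fundus exam can go untabulated

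*SAP*

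**What the plan says.** Protocol 7.1.9 asks that every attempt be made to bring back a subject who leaves early, so that the subject "completes the Visit 7 (End of Study; Early Termination) assessments before being discharged from the study". Protocol 7.1.7 lists those assessments. They include BCVA, slit lamp, IOP and dilated ophthalmoscopy.

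SAP 9.7.1.6 then limits the use of these data. In by-visit safety summaries, "data collected using Early Termination eCRFs will not be summarized unless the termination occurred within the visit windows of a particular visit". The next line adds: "All visits will be included in listings". The paragraph before it states: "All data, including data after rescue therapy, will be summarized as observed and no data imputation will be performed".

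The Visit Windows paragraph of SAP 9.7.1 sets two general rules. The first is "The nominal visits listed in the CRF will be used in the summaries". The second is "In general, unscheduled visits will not be summarized in tables unless otherwise noted".

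The exam-specific sections make no exception for slit lamp, fundus or IOP. SAP 9.7.1.6.4 says that fundus categories and shifts "will be tabulated at each scheduled visit for the study eye and non-study eye". SAP 9.7.1.6.3 uses the same layout for slit lamp, and SAP 9.7.1.6.5 gives IOP descriptive statistics by scheduled visit. Only SAP 9.7.1.6.6 goes further: it counts BCVA losses of three or more lines at a final visit as well as at each visit.

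In the schedule (Protocol Appendix 1; SAP Appendix I), slit lamp and IOP fall at Visit 1 and Visits 3 to 7. Dilated ophthalmoscopy falls at Visits 1 and 7 only.

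**The concern.** Safety is the secondary objective. The exit exam of a subject who leaves, and an exam done because something seemed wrong, may carry more safety information than a routine visit. Under the two rules, exit exams outside the windows and, in general, unscheduled exams do not enter the treatment-group summaries. A listing shows the result but gives no count by group.

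Fundus is the clearest case, because no post-dose exam is scheduled before Visit 7. If the exit exam has no row, that subject adds nothing after baseline to the fundus shift or cup-to-disc tables. For slit lamp and IOP the loss is smaller: earlier scheduled results stay in the tables and only the exit or unscheduled record is missing.

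IOP deserves a mention because Protocol 1.3.1 reports abnormal IOP tests in 2 of 30 phase 1 subjects, transient and judged related to the product. Fixed visits can miss short-lived changes that an unscheduled exam may catch. That figure gives context and does not measure the size of this gap.

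**Working it through.** **1. Visit windows.** From the schedule in both documents:
- Visit 4: Day 3 ± 1 = Days 2–4 (3 days)
- Visit 5: Day 7 ± 1 = Days 6–8 (3 days)
- Visit 6: Day 14 ± 2 = Days 12–16 (5 days)
- Visit 7: Day 21 ± 2 = Days 19–23 (5 days)

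Days 2 to 18, before the Visit 7 window opens, number 17. Days inside a window: 3 + 3 + 5 = 11. Days in no window: 17 − 11 = 6, namely Days 5, 9, 10, 11, 17 and 18. Share uncovered: 6/17 = 35%.

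**2. Where each kind of result goes**

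| Source of the exam | Slit lamp, IOP | Fundus |
|---|---|---|
| Scheduled visit held late | Tabulated under its nominal visit | Same (Visit 7) |
| Early termination, Days 19–23 | Tabulated | Tabulated |
| Early termination inside the Visit 4, 5 or 6 window | Tabulated | Admitted by the rule, but no fundus exam is scheduled at these visits; the SAP does not say where it goes |
| Early termination on Days 5, 9–11, 17, 18 | Listing only | Listing only |
| Unscheduled visit | In general, listing only | In general, listing only |

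**3. Number of drop-outs the plan implies.** SAP 9.7.2 gives 30 completers per group, 10% drop-out and a total of about 102. This reproduces: 30/(1 − 0.10) = 33.3, rounded up to 34 per group, and 3 × 34 = 102. Implied drop-outs: 0.10 × 102 = 10.2, or 102 − 90 = 12.

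**4. Number affected, slit lamp and IOP.** The documents give neither the day of exit nor the share of leavers who attend an exit exam. Assume that exits are uniform over Days 2 to 18 and that every leaver has an exit exam:
- 10 leavers: 10 × 6/17 = 3.5
- 12 leavers: 12 × 6/17 = 4.2, or 4.2/3 = 1.4 per group

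Without the uniformity assumption, the range runs from 0 (all exits inside windows, or no exit exams) to 12 (all exits on uncovered days, all examined).

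**5. Number affected, fundus.** The same 3.5 to 4.2 have an exam outside every window. If the Visit 4 to 6 windows turn out to have no fundus row either, the number rises to all who exit before Day 19 with an exam, which cannot exceed the 10 to 12 implied drop-outs.

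**6. What the AE tables recover.** The fundus sections (Protocol Appendix 7; SAP 9.5.1.4.6) record a shift to abnormal and clinically significant as an AE, and SAP 9.7.1.6.1 tabulates AEs without regard to visit. A shift from normal to abnormal but not clinically significant is not recorded as an AE. No AE threshold is stated for cup-to-disc ratio, IOP or slit lamp grades.

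**The case against.** The case against is substantial.

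- **AEs.** AE tables use the whole Safety Analysis Set and are not tied to visits. They include events leading to drug discontinuation or study termination. A clinically significant fundus worsening at exit therefore reaches a group table. This stands, and it covers the most serious fundus findings. It does not cover lesser shifts or cup-to-disc ratio. For IOP and slit lamp, capture depends on the investigator's judgement.
- **Leaving treatment is not leaving the study.** Protocol 5.5.2 asks that rescued subjects be kept for safety evaluation even off product, and Protocol 6.1 provides for follow-up after withdrawal of product for an AE. Those who stay attend nominal visits and remain in the tables. This stands and should keep the number of exit exams down.
- **Listings.** All visits are listed, and listings for about 102 subjects can be read through. True, but a listing gives no summary by group.
- **The count is soft.** Drop-outs include subjects lost to follow-up, who may have no exit exam to omit. This stands: the figure of about 4 is illustrative and leans high on exam attendance.
- **No safety tests are planned** unless otherwise specified, so the effect is on descriptive rows. This also stands.
- **A worst-value row has its own bias,** because subjects examined more often have more chances of an extreme value. This is right, and it is why that row is only optional below.

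**Conclusion.** The gap is real but narrow. Slit lamp, IOP and fundus results from early-termination visits outside every window, and in general from unscheduled visits, are kept out of the by-visit tables, and no last-value summary makes up for it. For fundus, the exit exam is normally the leaver's only post-dose exam. It is untabulated on the six uncovered days and has no assigned row in the Visit 4 to 6 windows. The size is about 4 subjects at most for slit lamp and IOP if exits are uniform over Days 2 to 18; actual exit timing and exam attendance are unknown.

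Four stronger readings are tempting, and the documents do not support them:
- A reader might infer that no early terminator's fundus exam is tabulated. Exits on Days 19 to 23 are, and for the earlier windows the SAP is silent, which is not the same as excluding them.
- A reader might infer that every out-of-window slit lamp or IOP result is lost. A scheduled visit held late stays under its nominal visit.
- A reader might infer that unscheduled visits are never summarised. The rule is general and leaves room for exceptions; none is made for these exams.
- A reader might infer that the tables favour one dose. That needs more safety withdrawals on that dose, and nothing in the documents shows this.

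**What to change.** In SAP 9.7.1.6.3, 9.7.1.6.4 and 9.7.1.6.5, add a last on-study value row that includes early-termination exams, in line with the BCVA final-visit count. For fundus, state that the Visit 7 or early-termination exam feeds this row; that also settles where an exit exam in the Visit 4 to 6 windows goes. The SAP does not define final visit for BCVA, so the same definition should be given there.

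Optionally, add a worst post-baseline row that includes unscheduled exams, with worst defined for IOP as the highest post-baseline value.

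Leave the nominal-visit rows unchanged. Note the exception in the Visit Windows paragraph and in SAP 9.7.1.6, where it should also be reconciled with the statement that all data are summarised as observed.

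The cost is SAP wording and a few table rows. The exit exams are already provided for in the protocol, and neither the sample size nor any existing row changes. The added rows mix exam days, and a worst-value row gives subjects with more exams more chances of an extreme result. Footnotes to the tables should say so.
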